## 4 STUDY POPULATION

For Parts A and B: healthy young adult male (19 to 45 years old) or healthy elderly male or post-menopausal female (over 60 years old).

The study population will consist of healthy subjects. Subjects must be able to provide written consent and meet all the inclusion criteria and none of the exclusion criteria.

Waivers for inclusion/exclusion criteria will not be granted.

### 4.1 Inclusion Criteria

Subjects will be entered into this study only if they meet all of the following criteria:

1. Institutional Review Board (IRB)/Independent Ethics Committee (IEC) approved written informed consent and privacy language as per national regulations must be obtained from the subject prior to any study-related procedures (including withdrawal of prohibited medication, if applicable).
2. Male subject should be 19 to 45 years old (for young adult cohorts) or over 60 years old (for elderly cohorts).
3. Subject has a body mass index (BMI) range of 18.5 to 30 kg/m^2 inclusive at Screening.
4. Male subject and his female spouse/partner who is of childbearing potential must be using highly effective contraception consisting of 2 forms of birth control (at least one of which must be a barrier method) starting at Screening and continuing throughout the study period and for 90 days after final study drug administration. Highly effective contraception is defined as:
  - Established use of oral, injected, or implanted hormonal methods of contraception
  - Placement of an intrauterine device or intrauterine system
  - Barrier methods of contraception: condom with spermicidal foam, gel, film, cream, suppository or occlusive cap (diaphragm or cervical/vault caps) with spermicidal foam, gel, film, cream, or suppository
5. Male subject must not donate sperm starting at Screening, throughout the study period and for at least 90 days after final study drug administration.
6. Female subject must be over 60 years old and post-menopausal (defined as at least 1 year without any menses) prior to Screening.
7. Subject agrees not to participate in another investigational study while on study treatment.

### 4.2 Exclusion Criteria

Subjects will be entered into this study only if they meet none of the following criteria:

1. Subject has a known or suspected hypersensitivity to KM-819, or any components of the formulation(s) used.
2. Subject has previously participated in a clinical study with KM-819.

3. Subject has any of the liver enzymes (aspartate aminotransferase [AST], alanine transaminase [ALT], alkaline phosphatase,  $\gamma$ -glutamyl transferase) or total bilirubin (TBIL) above the ULN. If any liver enzyme is  $> 1 \times$  ULN but  $< 1.5 \times$  ULN, the assessment may be repeated once during the Screening period or on check-in. If the repeated assessment is above the ULN, it is exclusionary. If the initial value is  $> 1.5 \times$  ULN, it cannot be repeated and is exclusionary.
4. Subject has any clinically significant history of allergic conditions (including drug allergies, asthma, eczema, or anaphylactic reactions, but excluding untreated, allergic rhinitis or rhino-conjunctivitis, or house dust mite allergy at time of dosing).
5. Subject with a history of a suicide attempt or suicidal behavior. Any recent suicidal ideation (a level of 4 or 5) within the last 3 months, or having a positive C-SSRS at check-in (Day -1), or who is at significant risk to commit suicide, as judged by the Investigator using the C-SSRS at Screening.
6. Subject has/had febrile illness or symptomatic viral, bacterial (including upper respiratory infection) or fungal (non-cutaneous) infection within 1 week before site check-in.
7. Subject has any clinically significant abnormality following the Investigator's review of the physical examination, ECG, and protocol-defined clinical laboratory tests at Screening or site check-in.
8. Subject has a mean pulse  $< 40$  or  $> 90$  beats per minute (bpm); mean systolic blood pressure (SBP)  $> 140$  mmHg; or mean diastolic blood pressure (DBP)  $> 90$  mmHg (measurements taken in triplicate after subject has been resting in the supine position for 5 minutes; pulse will be measured automatically) at Screening or check-in. If the mean pulse, mean SBP, or mean DBP is out of the range specified above, 1 additional triplicate measurement may be taken at Screening and check-in.
9. Subject has a mean QTcF interval of  $> 430$  msec (for males) and  $> 450$  msec (for females) at Screening or check-in. If the mean QTcF exceeds the limits above, 1 additional triplicate ECG can be taken. If this triplicate also gives an abnormal result, the subject should be excluded.
10. Subject has a history of unexplained syncope, cardiac arrest, unexplained cardiac arrhythmias or *torsade de pointes*, structural heart disease, or a family history of Long QT Syndrome.
11. Subject has use of any prescribed or non-prescribed drugs (including vitamins, hormone replacement therapy, natural and herbal remedies, e.g., St. John's Wort) in the 2 weeks before study drug administration. Acetaminophen up to 2000 mg/day is allowed.
12. Subject has had any use of tobacco- or nicotine-containing products within 6 months prior to Screening.
13. Subject has history of consuming more than 14 units of alcoholic beverages per week within 6 months prior to Screening or has a history of alcoholism or abuse of amphetamines, barbiturates, benzodiazepines, cannabinoids, cocaine, and opiates (drugs-of-abuse) within the past 2 years prior to Screening (Note: 1 unit = 355 mL of beer, 118 mL of wine, or 29 mL of spirits/hard liquor) or the subject tests positive at Screening or site admission for alcohol or drugs-of-abuse.
14. Subject has used any drugs-of-abuse within 3 months before check-in.

15. Subject has used any inducers of metabolism (e.g., barbiturates, rifampin) in the 3 months prior to check-in.
16. Subject has any significant blood loss, donated 1 unit (450 mL) of blood or more, or received a transfusion of any blood, or blood products within 60 days or donated plasma within 7 days before check-in.
17. Subject has a positive serology test for hepatitis B surface antigen (HbsAg), anti-hepatitis A virus Immunoglobulin M (HAV IgM), anti-hepatitis C virus (HCV Ab), or anti-human immunodeficiency virus (HIV Ab).
18. Subject has participated in any interventional clinical study or has been treated with any investigational drugs within 3 months or 5 half-lives, whichever is longer, before the initiation of Screening.
19. Subject has (recent history of) any other condition which, in the opinion of the Investigator, precludes the subject's participation in the trial.
20. Subject is an employee of the Kainos Medicine, Inc. or vendors involved in the study.

#### Additional Exclusion Criteria for Young Adult Subjects

21. For young adult cohorts, subject has any history or evidence of any clinically significant cardiovascular, gastrointestinal, endocrinologic, hematologic, hepatic, immunologic, metabolic, urologic, pulmonary, neurologic, dermatologic, psychiatric, renal, and/or other major disease or malignancy, as judged by the Investigator or designee.

#### Exclusion Criteria for Elderly Subjects

##### Replacement for Exclusion No. 8 above

8. Subject has a mean pulse < 50 or > 90 bpm; mean SBP > 160 mmHg; mean DBP > 100 mmHg (measurements taken in triplicate after subject has been resting in supine position for 5 minutes; pulse will be measured automatically).

##### Replacement for Exclusion No. 21 above

21. For elderly cohorts, subject has any history or evidence of any clinically significant cardiovascular, gastrointestinal, endocrinologic, hematologic, hepatic, immunologic, metabolic, urologic, pulmonary, neurologic, dermatologic, psychiatric, renal, and/or other major disease or malignancy that is not well managed and stable, as judged by the Investigator or designee.

#### Additional Exclusion Criteria

22. Elderly subject is excluded if the Glomerular Filtration Rate (calculated based on Cockcroft-Gault formula) is < 60 mL/min/1.73 m^2.
23. Clinically significant abnormal findings in the lumbar X-ray examination (only for elder subjects for MAD study).

#### 4.3 Subject Withdrawal and Replacement

A subject may withdraw from the study at any time without penalty and for any reason without prejudice to his/her future medical care. Participation of subjects may also be discontinued based on the medical judgment of the PI in conjunction with the Sponsor for any of the following reasons:

- ECG abnormalities:  
Any increases in QTcF > 500 msec or increase > 60 msec from baseline as confirmed with 3 consecutive ECGs taken within 5 minutes, with at least a 1-minute interval.
- Suicidality:  
Any suicide attempt or any recent suicidal ideation (a level of 4 or 5) since the last assessment, or a significant risk to commit suicide, as judged by the PI using the C-SSRS.
- Liver Safety Monitoring:  
Please refer to Stopping Criteria No. [2](#).
- After enrolment, the subject is found to violate the inclusion and/or exclusion criteria
- AE(s)
- Subject lost to follow-up
- Major protocol violation
- Use of prohibited medications mentioned in Section [5.8](#)
- The Investigator may, after discussion with the subject, withdraw the subject due to any serious safety concerns
- The study is terminated prematurely
- Other

In all cases, the reason(s) for withdrawal, and the primary reason, must be recorded on the electronic case report form (eCRF). Subjects who are withdrawn will have an Early Discontinuation (ED) Visit per the Schedules of Assessments (see Table [7-1](#) and Table [7-2](#)).

A subject may also be withdrawn from study by the Sponsor, Regulatory Authorities, or IECs/IRBs.

Subjects will also be withdrawn if the entire study is terminated prematurely as described in Section [9.10](#).

Withdrawn subjects may be replaced at the discretion of the Sponsor with agreement of the Investigator. Subjects who are discontinued because of treatment-emergent AE (TEAE) or possible toxic effects of the drug will not be replaced.

#### 4.4 Planned Sample Size and Number of Study Centers

It is planned to recruit in total 72 healthy young adult subjects and 16 healthy elderly subjects at 1 center in Korea for this study.

Part A: up to 40 healthy young adult male and 8 healthy elderly male or post-menopausal female subjects will be enrolled.

Part B: up to 32 healthy young adult male and 8 healthy elderly male or post-menopausal female subjects will be enrolled.

See Section 8.10 for a discussion of sample size.

## 4.5 Subject Identification and Randomization

### 4.5.1 Subject Identification

Upon enrolment, each subject will receive a unique screening number. Enrolled subjects who drop out of the study before randomization will retain their screening number.

### 4.5.2 Randomization Scheme

In each dose cohort, 8 subjects will be randomized to have 6 subjects receiving KM-819 and 2 subjects receiving placebo in both Part A and Part B.

In each single dose cohort (Part A), dosing of subjects will be sentinel, i.e., 2 subjects will be dosed on the first day (1 subject will receive active treatment and 1 subject will receive placebo) and the remaining 6 subjects will be dosed at least 24 hours after the first 2 subjects.

Randomization will occur on Day 1 (of the first treatment period for Part A) after all predose procedures have been performed and eligibility for the clinical study has been confirmed. Each eligible subject will receive a 4-digit randomization number. Randomization numbers will be sequential and will be assigned as follows:

Part A:

Cohort 1: 1101-1108

Cohort 2: 1201-1208

Cohort 3: 1301-1308

Cohort 4: 1401-1408

Cohort 5: 1501-1508

Cohort 6: 1601-1608

Replacement subjects will be assigned the same randomisation number as the subject they are replacing plus 50, i.e., a subject replacing Subject 1101 will be assigned the subject number 1151.

Part B:

Cohort 1: 2101-2108

Cohort 2: 2201-2208

Cohort 3: 2301-2308

Cohort 4: 2401-2408

Cohort 5: 2501-2508

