### **3.5 Stopping Criteria for Dose Escalation**

Dosing will be stopped if 1 (or more) of the following apply. Depending on the nature of the AEs, it could be decided to investigate a lower dose level (intermediate between the current and the prior one) in the next group.

1. If 1 or more subjects experiences a study drug-related serious adverse event (SAE), unblinding of the subject(s) will be done. If the subject(s) was (were) on active treatment, dosing will be stopped.
2. If 2 subjects in 1 dose group show the following findings in 2 consecutive postdose measurements within 24 hours and if unblinding reveals that both subjects received active treatment, dosing will be stopped:
  - a. ALT or AST  $\geq 3 \times$  upper limit of normal (ULN) or,
  - b. ALT or AST  $\geq 2 \times$  ULN and ALT or AST  $\geq 5 \times$  baseline value or,
  - c. TBIL  $\geq 2 \times$  ULN
3. If 2 or more subjects in 1 cohort experience AEs of severe intensity or 4 or more subjects in 1 cohort experience AEs of moderate intensity, which are considered by the PI and/or Sponsor to be possibly or probably related to the investigational product, and of clinical concern, and if unblinding reveals that these subjects received active treatment, dosing will be stopped.

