##### *6.4.1.3.1 Seriousness*

A serious AE (SAE) is defined as any untoward medical occurrence that at any dose:

- Results in death;
- Is life-threatening;  
This means that the subject is at risk of death at the time of the event; it does not mean that the event hypothetically might have caused death if it were more severe;
- Requires inpatient hospitalization or prolongation of existing hospitalization;
- Results in persistent or significant disability or incapacity;
- Is a congenital anomaly or birth defect;
- Is an important medical event(s) that may not be immediately life-threatening or result in death or hospitalization but that may jeopardize the subject or require intervention to prevent one of the above outcomes. Examples of such events are intensive treatment in an emergency room or at home for allergic bronchospasm; blood dyscrasias or convulsions that do not result in hospitalization; or development of drug dependency or drug abuse.

Medical and scientific judgment should be exercised in deciding whether a case is serious and whether expedited reporting is appropriate.

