##### *6.4.1.3.2 Intensity*

The intensity of each AE must be assessed by the Investigator using one of the following categories, and recorded in the eCRF:

- Mild: The AE was transient and easily tolerated by the subject.
- Moderate: The AE caused discomfort and interferes with the subject's general condition.
- Severe: The AE caused considerable interference with the subject's general condition and may have been incapacitating.

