**Table 6-1: Causal Relationship of Adverse Event to Study Drug**

Causal relationship	Description
Definite	A clinical event with a plausible time relationship to drug administration and which cannot be explained by concurrent disease or other drugs or chemicals. Response to withdrawal plausible (pharmacologically, pathologically), Event definitive pharmacologically or phenomenologically (i.e., an objective and specific medical disorder or a recognized pharmacological phenomenon), Rechallenge satisfactory, if necessary.
Probable	A clinical event with a reasonable time relationship to drug administration is unlikely to be attributed to concurrent disease or other drugs or chemicals. Response to withdrawal clinically reasonable (Rechallenge not required).
Possible	A clinical event with a reasonable time relationship to drug administration, but which could also be explained by concurrent disease or other drugs or chemicals.
Unlikely	A clinical event whose time relationship to drug administration makes a causal connection improbable, which could be plausibly explained by underlying disease or other drugs or chemicals.
Not related	A clinical event with no time relationship to drug administration, or with no causal relationship to drug administration (e.g., definitely induced by the clinical conditions of the subject or by the test procedures/requirements or by external events which are not associated with study treatments).
Unassessable	A clinical event with insufficient or contradictory information to permit assessment and identification of the cause.

The causal relationship of definite, probable, possible and unassessable will be considered as related to study drug.

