#### 6.4.1.3.4 Adverse Events of Interest

An adverse event of interest (AEI) is an event which, in the evaluation of safety, has a special focus. An AEI is an AE (SAE or non-serious AE) which fulfils below defined AEI criteria:

- Potential Hy's law cases

Potential Hy's law, defined as  $\geq 3 \times$  ULN ALT with co-existing  $\geq 2 \times$  ULN bilirubin in the absence of  $\geq 2 \times$  ULN ALP, with no alternative explanation for the biochemical abnormality, must always be reported as an AE of interest (i.e., without waiting for any additional etiologic investigations to have been concluded). Follow-up information should then be reported if an alternative etiology is identified during investigation and monitoring of the subject.

AEI should be reported to the Sponsor/PAREXEL immediately (within 24 hours of the site being aware of the event).

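### Part A requires no review of the sentinel pair before the remaining six subjects are dosed, and a severe, related, non-serious AE in the one active sentinel meets no stopping criterion

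*Protocol*

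**What the plan says.** **Release.** The protocol synopsis, protocol Sections 3.1 and 4.5.2, and SAP Section 2 describe the step in the same way. Two subjects are dosed on the first day, one active and one placebo; then "the remaining 6 subjects will be dosed at least 24 hours after the first 2 subjects". None of these places names a reviewer, the data to be looked at, or a go/no-go decision.

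**Reviews.** Every written review is at the level of the cohort or dose:
- Section 1.4: after each dose level.
- Section 3.3: blinded PI and Sponsor review after each cohort.
- Section 3.4: the whole cohort through Day 4.
- Section 3.5.1: PK before the next dose.

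**Stopping (Section 3.5).** Criterion 1, a drug-related SAE on active treatment, can be met by one subject. Criterion 2 (liver tests) begins "If 2 subjects in 1 dose group show the following findings in 2 consecutive postdose measurements within 24 hours". Criterion 3 begins "If 2 or more subjects in 1 cohort experience AEs of severe intensity or 4 or more subjects in 1 cohort", the second limb being for moderate events. Criteria 2 and 3 both also require that unblinding show the subjects concerned were on active drug.

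**Definitions.** Section 6.4.1.3.2 describes a severe AE as one that considerably disturbed the subject's "general condition and may have been incapacitating". Seriousness is defined separately in Section 6.4.1.3.1. It covers, among others, an event that "Requires inpatient hospitalization or prolongation of existing hospitalization" and important medical events. Table 6-1 adds: "The causal relationship of definite, probable, possible and unassessable will be considered as related to study drug".

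**The concern.** Section 1.4 counts sentinel dosing among the safety practices that make this first-in-human study acceptable. A stagger protects the later subjects only if someone looks at the earlier ones and can stop. Here the looking is left unstated, and the criteria that deal with severe AEs and liver tests are counted over a whole cohort. That is reasonable for deciding on escalation, but these criteria cannot act when only one active subject has been dosed. At stake are up to five further active exposures at a dose that has just produced a severe related event in the only person who received it.

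**Working it through.** The plan gives no operating figure for the sentinel step, and cohort size is justified by convention (Section 8.10), so there is no stated number to reproduce. The check is of the rules, followed by a sizing on assumed rates.

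**1. Allocation (Section 4.5.2).** A cohort has 6 active and 2 placebo. The sentinels take 1 + 1, so the remaining six are 5 active and 1 placebo.

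**2. Which criteria can act at release, with one active subject dosed?**

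| Section 3.5 criterion | Active subjects needed | Active subjects dosed | Can act? |
|---|---|---|---|
| 1. Drug-related SAE | 1 | 1 | Yes |
| 2. Liver tests | 2 | 1 | No |
| 3. Severe related AEs | 2 | 1 | No |
| 3. Moderate related AEs | 4 | 1 | No |

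For criterion 3 (severe limb), P(X ≥ 2 with n = 1) = 0 at every event rate. The uncovered case is therefore an AE that is severe and related but not serious.

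**3. Size of the gap.** Let p be the chance of such an AE in an active subject at the dose in question. No document gives p, so a range is used, with subjects independent. Given a sentinel event, the expected number among the next five is 5p. A one-subject hold can avoid at most p × 5p = 5p² per cohort.

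| Assumed p | 5p, given a sentinel event | 5p² per cohort |
|---|---|---|
| 0.01 | 0.05 | 0.0005 |
| 0.05 | 0.25 | 0.0125 |
| 0.10 | 0.50 | 0.05 |
| 0.20 | 1.0 | 0.20 |

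These figures hold p fixed. If p is uncertain, a sentinel event is itself evidence that p is high. With an assumed Beta(1,19) prior (mean 0.05), the mean after one event in one subject is 2/21 = 0.095. The next five would then be expected to yield 5 × 0.095 = 0.48 events rather than 0.25, and the avoidable number per cohort is 0.05 × 0.48 = 0.024 rather than 0.0125.

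**4. Unnecessary holds.** Let q be the assumed chance that a sentinel, active or placebo, has a severe AE judged at least possibly related but not caused by the drug. With two sentinels in each of k cohorts, P(at least one such hold) = 1 − (1 − q)^(2k).

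| Assumed q | k = 5 | k = 6 |
|---|---|---|
| 0.005 | 4.9% | 5.8% |
| 0.01 | 9.6% | 11.4% |
| 0.02 | 18.3% | 21.5% |

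The k = 6 column applies if the elderly single-dose cohort is also sentinel-dosed. Sections 1.4 and 4.5.2 imply that it is; Section 3.1 and SAP Section 2 mention only five cohorts.

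**5. Would a look at 24 h be informative?** Section 5.3 predicts a half-life of 9.27 h, so 24 / 9.27 = 2.6 half-lives. With fast absorption, 1 − 2^(−24/9.27) = 0.83 of the exposure has passed. Table 7-1 already provides AE assessment, vital signs at 0.5, 1, 2 and 4 h, a triplicate ECG at 1 h, and Day 2 vital signs and ECG with no clock time.

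**The case against.** The strongest reply is that the gap is what remains after several safeguards, and that competent staff would close it.

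- **Criterion 1 is broad.** Prolonged hospitalization and important medical events count as serious, and possible or unassessable causality counts as related. Many alarming sentinel events would stop dosing. A reader might infer that release depends on the clock and nothing else; the documents do not support that. What stands is the narrower case of a severe, related event that meets no SAE definition.
- **Nothing compels dosing at 24 h.** The interval is a minimum, so an open-ended pause complies. This is correct, but it permits a pause without requiring one, and Section 9.8 says the protocol is to be followed exactly.
- **Other clauses exist.** Section 4.3 says "Participation of subjects may also be discontinued based on the medical judgment of the PI in conjunction with the Sponsor", but that concerns the affected subject, who in Part A has already had the only dose. Section 6.4.1.3.4 requires prompt reporting of a single potential Hy's law case, and Section 9.12 requires notification of a significant safety issue. Section 9.10 allows termination of the study. None is a hold on the six.
- **The benefit is small.** Over five cohorts, 5 × 5p² is 0.0025 at p = 0.01 and 0.0625 at p = 0.05, against a 5% to 18% chance of an unnecessary hold. The starting dose is 56-fold below the calculated maximum recommended starting dose, so a high p at the early doses has no support in the documents. This stands and limits how strongly the point can be pressed. The two sides are not like for like, however: one is a severe reaction, the other a postponed dosing morning.

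**Conclusion.** The point holds in a narrow form. No sentinel review is required before release, and one foreseeable type of event in the active sentinel triggers no written hold. Up to five more active doses could follow under the plan as written. Five is the upper case: no text says the six are dosed together, and if they were staggered, criterion 3 could act on the second severe active case. The avoidable number is at most 5p² per cohort at a given p. It is smaller if the PI would have paused anyway and somewhat larger if uncertainty about p is allowed for. Both p and q are assumptions, and subjects are taken as independent.

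A reader might also infer that the gap is urgent because the top dose is predicted to exceed the dog NOAEL exposure. On the Section 5.3 parameters, predicted AUC is 0.35 × 400 / 2.93 = 47.8 ug.h/mL at 400 mg, above the 41.3 limit in Section 3.5.1 (at 200 mg it is 23.9). But even with instantaneous absorption, predicted Cmax at 400 mg is only 0.35 × 400 / 39.2 = 3.6 ug/mL, against a limit of 9.3. Section 3.5.1 also governs that step using observed human data. The exposure predictions therefore do not make this a serious flaw. It is a low-cost improvement worth making.

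**What to change.** Add to Sections 3.1 and 4.5.2, and mirror in SAP Section 2:

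- The remaining six are dosed only after the PI, still blinded, has reviewed and documented both sentinels' AEs, vital signs and ECGs. The review includes any Day 2 laboratory results already back, without waiting for those still outstanding.
- The sentinels' scheduled Day 2 vital signs and ECG are timed before that release.
- Dosing is held pending PI and Sponsor review if either sentinel has a severe AE considered at least possibly related.

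Because the trigger applies to either sentinel, the hold itself needs no unblinding. If the review does lead to unblinding one sentinel, the other is revealed too, since the pair is 1 + 1.

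**Cost.** The change needs protocol wording and one signed release form per cohort, with no added sample or visit. With no trigger, the 8:00 to 10:00 dosing window and the Day -1 baseline are unchanged. The downside is an occasional hold for a placebo or unrelated event, at the rates shown above. If the six are to be dosed at about 24 h, a hold would normally come after their Day -1 check-in. Their dosing then moves to a later morning, the Day -1 assessments are repeated or become an older baseline, and the 28-day screening limit must be watched.
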